are no records with indeterminant test result, then select those with unavailable result ('NOT EVALUABLE). If there are no records with unavailable test result, then select those with not reported or not available result (all other records). The latest record will be used as the baseline in the analyses. If there is more than one record for the latest date, then choose the one with the greatest specimen ID.

- Post baseline period:
 - On-treatment AEs will be defined as AEs with an onset date and time on or after the date and time of the first dose of study treatment (or with an onset date on or after the day of first dose of study treatment if time is not collected or is missing). For subjects who are off study treatment, AEs will be included if event occurred within a safety window of 30 days (or 100 days depending on the analysis) after the last dose of study treatment. No "subtracting rule" will be applied when an AE occurs both pre-treatment and post-treatment with the same preferred term and grade.
 - On-treatment evaluations (laboratory tests, pulse oximetry and vital signs) will be defined as evaluations taken after the day (and time, if collected and not missing) of first dose of study treatment. For subjects who are off study treatment, evaluations should be within a safety window of 30 days (or 100 days depending on the analysis) after the last dose of study treatment.
- For subjects who are off study treatment safety assessments will only be collected through 100 days post last dose.

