7.6.6 Select Adverse Events

Analyses will be performed by select AE category.

7.6.6.1 *Incidence of Select AE*

Select AEs will be summarized by treatment group for each category/subcategory.

The following analyses will be conducted using the 30-day safety window only:

- Overall summaries of any select AEs by worst CTC grade (any grade, grade 3-4, grade 5) presented by Category or Subcategory/PT.
- Overall summaries of any drug-related select AEs by worst CTC grade (any grade, grade 3-4, grade 5) presented by Category or Subcategory/PT.

A by-subject select AE listing will be provided.

7.6.6.2 *Time-to Onset of Select AE*

Not Applicable.

7.6.6.3 *Time-to Resolution of Select AE*

Not Applicable.

7.6.7 *Immune-Mediated Adverse Events*

IMAEs will be summarized by treatment group for each immune-mediated category / PT using the 100-day safety window:

- Overall summary of non-endocrine IMAEs by worst CTC grade (any grade, grade 3-4, grade 5) where immune modulating medication was initiated presented by Category / PT.
- Overall summary of endocrine IMAEs by worst CTC grade (any grade, grade 3-4, grade 5) presented by Category / PT.

A by-subject listing of IMAEs will be provided. By-subject listings of time-to resolution for longest IMAEs cluster (any grade and grade 3-5 in separate summaries) will also be provided.

7.6.8 *Other Events of Special Interest*

A by-subject listing of OEOSI will be provided.

7.6.9 *Multiple Events*

Not applicable.

7.6.10 *Laboratory Parameters*

The analysis population for each laboratory test is restricted to treated subjects who underwent that laboratory test. Laboratory tests (in addition to the tests specified below) with CTC criteria collected in the specific studies may also be included in the summaries.

7.6.10.1 *Hematology*

The following will be summarized by treatment group as worst CTC grade on-treatment per subject and as shift table of worst on-treatment CTC grade compared to baseline CTC grade per

subject: hemoglobin (HB), platelets, white blood counts (WBC), absolute neutrophils count (ANC) and lymphocyte count (LYMPH).

The analyses will be conducted using the 30-day safety window.

A by-subject listing of these laboratory parameters will be provided.

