8 CONVENTIONS

The following conventions may be used for imputing partial dates for analyses requiring dates:

- For missing and partial adverse event onset dates, imputation will be performed using the Adverse Event Domain Requirements Specification²
- For missing and partial adverse event resolution dates, imputation will be performed as follows:
 - If only the day of the month is missing, the last day of the month will be used to replace the missing day. If the imputed date is after the death date or the last known alive date, then the latest known alive date or death date is considered as the resolution date.
 - If the day and month are missing or a date is completely missing, it will be considered as missing.
- Missing and partial non-study medication domain dates will be imputed using the derivation algorithm described in 4.1.3 of BMS Non-Study Medication Domain Requirements Specification³.
- For death dates, the following conventions will be used for imputing partial dates:
 - If only the day of the month is missing, the 1st of the month will be used to replace the missing day. The imputed date will be compared to the last known alive date and the maximum will be considered as the death date.
 - If the month or the year is missing, the death date will be imputed as the last known alive date.
 - If the date is completely missing but the reason for death is present, the death date will be imputed as the last known date alive.
- For date of progression to prior therapies, the following conventions will be used for imputing partial dates:
 - If only the day of the month is missing, the 1st of the month will be used to replace the missing day.
 - If the day and month are missing or a date is completely missing, it will be considered as missing.
- For other partial/missing dates, the following conventions were used:
 - If only the day of the month is missing, the 15th of the month will be used to replace the missing day.
 - If both the day and the month are missing, “July 1” will be used to replace the missing information.
 - If a date is completely missing, it will be considered as missing.

The following conversion factors will be used to convert days to months or years:

$$1 \text{ month} = 30.4375 \text{ days} \text{ and } 1 \text{ year} = 365.25 \text{ days.}$$

Duration (e.g. time-to onset, time-to resolution) will be calculated as follows:

$$\text{Duration} = (\text{Last date} - \text{first date} + 1)$$

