Last known alive date will be defined based on all appropriate dates collected on the CRF.

All statistical analyses will be carried out using SAS (Statistical Analysis System software, SAS Institute, North Carolina, USA) unless otherwise noted.

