10 DOCUMENT HISTORY

Table 10-1: Document Revision History

Version Number	Author(s)	Description
1.0	[name]	Initial release dated 19-Oct-2019

APPENDIX 1 TIME-TO ONSET AND TIME-TO RESOLUTION DEFINITION AND CONVENTIONS FOR SELECT ADVERSE EVENTS, IMMUNE-MEDIATED ADVERSE EVENTS AND EVENTS OF SPECIAL INTEREST

Time-to onset definition

Time-to onset of AE (any grade) for a specific category is defined as the time between the day of the first dose of study treatment and the onset date of the earliest AE (of any grade) in this category.

The time-to onset of AE (grade 3-5) for a specific category is defined similarly with an onset date corresponding to a grade 3-5 AE.

Time-to onset of drug-related AE (any grade or grade 3-5) for a specific category is defined similarly but restricted to drug-related AE.

Time-to onset for a specific subcategory is defined similarly but restricted to event of this subcategory.

Time-to resolution definition

In order to derive the time-to resolution, overlapping or contiguous AEs within a specific category or subcategory will be collapsed into what will be termed “clustered” AEs. For example, if a subject (without pre-treatment AE) experienced an AE from 1st to 5th January, another AE (with different PT but within same category) from 6th to 11th January and same AE from 10th to 12th January, these will be collapsed into one clustered AE from 1st to 12th January. [Appendix Table 1](#) is summarizing key derivation steps for each type of clustered AEs.

Time-to resolution of AE (any grade) for a specific category is defined as the longest time from onset to complete resolution or improvement to the grade at baseline among all clustered AEs experienced by the subject in this category per adverse event criteria category. Events which worsened into grade 5 events (death) or have a resolution date equal to the date of death are considered unresolved. If a clustered AE is considered as unresolved, the resolution date will be censored to the last known alive date. Improvement to the grade at baseline implies that all different events in the clustered adverse event should at least have improved to the corresponding (i.e. with same preferred term) baseline grade. This measure is defined only for subjects who experienced at least one AE in the specific category.

The time-to resolution of AE (grade 3-5) for a specific category is defined similarly with an onset date corresponding to a grade 3-5 AE.

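### Unresolved AE clusters are censored at the last known alive date, which can fall after AE collection has ended at 100 days post last dose (minor)

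*SAP*

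**What the plan says.** The rule is in Appendix 1, under the time-to resolution definition: "If a clustered AE is considered as unresolved, the resolution date will be censored to the last known alive date". The measure itself is "defined as the longest time from onset to complete resolution or improvement to the grade at baseline among all clustered AEs" in a category, so one cluster per subject and category is carried forward.

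The censoring date is defined in Section 8: "Last known alive date will be defined based on all appropriate dates collected on the CRF". Nothing ties it to the safety window.

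The end of safety data collection is in Section 5.1: "For subjects who are off study treatment safety assessments will only be collected through 100 days post last dose".

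Section 4.1 names time to resolution of immune-related AEs among the safety endpoints. Section 7.6.6.3 marks the analysis for select AEs as not applicable. That leaves Section 7.6.7, which works on the same window ("IMAEs will be summarized by treatment group for each immune-mediated category / PT using the 100-day safety window") and gives the only output: "By-subject listings of time-to resolution for longest IMAEs cluster (any grade and grade 3-5 in separate summaries) will also be provided".

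Section 7.1.1 treats follow-up time differently when it defines person-years. With the 100-day window, exposure stops 100 days after last dose for a subject followed that long. The last known alive date is used only for subjects still on treatment or followed for less time.

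**The concern.** A censoring time should be the last moment at which the event, here resolution, could have been seen. Knowing that a subject is alive does not tell us whether an AE is still present. If AE collection stops 100 days after last dose and the subject is known to be alive later, the time in between carries no information on resolution, yet Appendix 1 counts it as time unresolved.

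Two things are at stake in the Section 7.6.7 listings. The censored length shown for an unresolved IMAE can be longer than the time observed. And because the longest cluster is chosen on that length, an unresolved cluster can be listed in place of one whose resolution was observed.

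**Working it through.** **Check of the clustering rule.** The SAP gives no time-to-resolution figure to reproduce. Its clustering example does reproduce: records of 1–5, 6–11 and 10–12 January collapse into one cluster of 1–12 January.

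**Inputs from the SAP**
- Duration = last date − first date + 1 (Section 8).
- End of AE collection = last dose + 100 days (Section 5.1).
- Censoring date for an unresolved cluster = last known alive date (Appendix 1).

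**Formula.** Let L be the day of last dose and K the last known alive day. For a cluster with onset on day s, the rule gives K − s + 1. The part covered by AE collection is min(K, L + 100) − s + 1. The difference is max(0, K − (L + 100)).

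**Size for an assumed onset 3 days after last dose (s = L + 3)**

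| Last known alive date | Length under Appendix 1 | Length within AE collection | Excess |
|---|---|---|---|
| L + 50 | 50 − 3 + 1 = 48 | 48 | 0 |
| L + 100 | 100 − 3 + 1 = 98 | 98 | 0 |
| L + 150 | 150 − 3 + 1 = 148 | 98 | 50 |
| L + 200 | 200 − 3 + 1 = 198 | 98 | 100 |
| L + 300 | 300 − 3 + 1 = 298 | 98 | 200 |

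**How large the gap could be.** Assume a first dose on 15-Oct-2018 and a subject known to be alive on the SAP date, 19-Oct-2019. That is 369 days later, or study day 370.
- Only day 1 given: 370 − (1 + 100) = 269 days.
- Last dose on w9d1 (8 × 7 + 1 = day 57): 370 − (57 + 100) = 213 days.
- Full nivolumab course: the SAP does not give the interval before the first 480 mg dose. If it is 3 weeks, the last dose is day 57 + 21 + 5 × 28 = 218 and the gap is 370 − 318 = 52 days. If it is 4 weeks, the last dose is day 225 and the gap is 370 − 325 = 45 days.

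If no contact was recorded after the window, the gap is 0. Earlier enrolment could make it larger.

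**Choice of the longest cluster.** The choice changes only if an observed, resolved cluster in the same category is longer than the capped length and shorter than the uncapped one. Take L = 218, an unresolved cluster with onset on day 221, and a resolved cluster from day 60 to day 179 (179 − 60 + 1 = 120 days). With K = 218 + 150 = 368, Appendix 1 gives the unresolved cluster 368 − 221 + 1 = 148 days, so it is listed. With the cap it has 318 − 221 + 1 = 98 days, and the observed 120-day cluster is listed instead.

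This needs room before the unresolved onset, because overlapping or contiguous records are collapsed. With L = 57 and onset on day 60, an earlier separate cluster could run at most from day 1 to day 58. That is 58 days, below 98, so the choice would not change. Displacement is therefore a narrower problem than the excess length.

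**The case against.** **Ongoing AEs may be followed for longer.** Section 5.1 speaks of safety assessments. It does not say that an AE already reported and still open is no longer followed, and the protocol, which was not available for this review, may require that. Section 8 also bounds an imputed partial AE resolution date by the last known alive date or death date, not by the window. This stands as a reason not to impose a rigid cut at 100 days. It does not rescue the present rule: the word *only* in Section 5.1 is plain, and the Section 8 convention concerns resolution dates that were at least partly recorded, not clusters with no resolution.

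**The gap may be rare.** Section 2.4 records that Revised Protocol 03 removed efficacy follow-up, which makes late contacts less likely. This stands. Late dates are still possible, since Section 7.6.1 reports all deaths beside those within 100 days, which suggests that vital status may be known after the window.

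**The value is censored.** A reader might infer that the plan reports unobserved time as continuing toxicity. It does not: the value is a censored one with status unresolved, not a completed duration. The fault is only that the censoring time can exceed the observed time.

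**Arm bias.** A reader might also infer that the distortion differs by arm, because the planned regimens end at different times. The SAP does not support this. It plans no Kaplan-Meier estimate, median or arm comparison of resolution time. In addition, Section 5.3 counts placebo recipients as treated and Section 7.1.1 counts placebo in exposure, so control subjects dosed before unblinding may have a later last dose than the active control regimen suggests.

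**Conclusion.** The point holds in a limited form and is minor. Appendix 1 lets the censoring time run past the end of AE collection stated in Section 5.1. The excess is exactly the number of days by which the last known alive date exceeds last dose + 100, and zero otherwise. Under the assumptions above it could range from 0 to 269 days for a subject first dosed on 15-Oct-2018. The SAP gives no basis for saying how many subjects are affected.

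The reach is confined to the by-subject time-to-resolution listings in Section 7.6.7. The words about separate summaries there distinguish any grade from grade 3–5 within listings and do not announce a summary statistic. The full IMAE listing is provided in any case, so a displaced cluster is not lost from the report. The rule would matter more if the exploratory analyses allowed by Section 9 used the censored times.

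The conclusion assumes that AE status is generally not recorded after the window, as Section 5.1 indicates. If the protocol follows open AEs for longer, the excess shrinks accordingly.

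**What to change.** In Appendix 1, replace the censoring sentence with a rule of this kind:

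*An unresolved clustered AE is censored at the earlier of (a) the last known alive date and (b) the end of AE collection. The end of AE collection is 100 days after the last dose of study treatment or, if later, the last date on which the status of an AE in the cluster was recorded. The longest cluster is selected on the length so obtained.*

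In Section 7.6.7, add a flag for censored values to the time-to-resolution listings.

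If the CRF holds no status date for open AEs, the 100-day limit applies by default. If open AEs are followed for longer, the later status date is used and no observed time is lost. The cost is one sentence in the SAP, one derivation change and one listing column. Some censored durations will become shorter, and in a few cases a different cluster may be listed as the longest.

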Appendix Table 1: Derivation of Clustered AE

Type of clustered AE	Derivation
Any grade	Collapse any on-treatment AE from the same category
Drug-related of any grade	Collapse any on-treatment drug-related AE from the same category
Grade 3-5	Collapse any on-treatment AE from the same category. Resolution will be based on the onset date of the earliest grade 3-5 records (if no grade 3-5 record, clustered AE is excluded)
Drug-related of Grade 3-5	Collapse any on-treatment drug-related AE from the same category Resolution will be based on the onset date of the earliest grade 3-5 record (if no Grade 3-5 record, clustered AE is excluded)

The algorithm for collapsing adverse event records is using the following conventions:

For each subject and specified category, the corresponding adverse event records will be collapsed when:

- 1) Multiple adverse event records have the same onset date.
- 2) The onset date of an event record is either the same day or 1 day later than the resolution date of a preceding event record (contiguous events).
- 3) The onset date of an event record is after the onset date and prior to or on the resolution date of a preceding event record (overlapping events).
